5.2. Exclusion Criteria

A subject will not be eligible for inclusion in this study if any of the following criteria apply:

CONCURRENT CONDITIONS/MEDICAL HISTORY (INCLUDES LIVER FUNCTION AND QTc INTERVAL)

All Groups:

1. Postmenopausal as defined by gynaecological history.
2. Chronic lung condition of any etiology including asthma, Chronic obstructive pulmonary disease (COPD), emphysema, interstitial lung disease or active Tuberculosis (TB).
Note: Childhood asthma (resolved) is not exclusionary.
3. Current or chronic history of liver disease, or known hepatic or biliary abnormalities (with the exception of Gilbert's syndrome or asymptomatic gallstones).
4. Blood pressure >140 systolic or >90 diastolic.

Group 1 Only:

5. Females with planned Caesarean Section.
6. Females with significant medical complications as determined by investigator.

Group 2 Only:

7. Currently breastfeeding or lactating.
8. QT duration corrected for heart rate by Fridericia's formula (QTcF) >450 milliseconds (msec).
9. Alanine aminotransferase (ALT) and bilirubin >1.5 Upper Limit of Normal (ULN) (isolated bilirubin >1.5xULN is acceptable if bilirubin is fractionated and direct bilirubin <35%).
10. Subjects with highly-active or symptomatic gynaecological disorders (such as large symptomatic fibroids).

CONCOMITANT MEDICATIONS

All Groups:

11. Prescription or non-prescription drugs not approved by the investigator (refer to Section 6.12.1 for approved medications).
12. Oxytocin for any reason (including, but not limited to, induction or augmentation of labour) prior to administration of study-related oxytocin.

RELEVANT HABITS**All Groups:**

13. History of regular alcohol consumption within 6 months of the study defined as:
- An average weekly intake of >14 units. One unit is equivalent to 8 grams (g) of alcohol: a half-pint (~240 milliliter [ml]) of beer, 1 glass (125 ml) of wine or 1 (25 ml) measure of spirits.
14. Current smokers or subjects with a history of smoking within 6 months of screening, or with a total pack year history of >5 pack years.
- a. Confirmatory use via a Smokerlyzer is at the discretion of the local investigator, but is advised if the subject's recent smoking history is in doubt.

CONTRAINDICATIONS**All Groups:**

15. History of sensitivity to any of the study medications, or components thereof, or a history of drug or other allergy that, in the opinion of the investigator or Medical Monitor, contraindicates their participation (e.g. allergy to any previous inhaler use).
16. Participation in another clinical trial, which in the opinion of the investigator, jeopardizes the subject's safety or study outcomes.

DIAGNOSTIC ASSESSMENTS AND OTHER CRITERIA**All Groups:**

17. Where participation in the study would result in donation of blood or blood products in excess of 500 mL within 56 days.
18. The subject has participated in a clinical trial and has received an investigation product within the following time period prior to the first dosing day in the current study: 30 days or twice the duration of the biological effect of the investigational product (whichever is longer).
19. Exposure to more than four new chemical entities within 12 months prior to the first dosing day.

Group 2 Only:

20. Presence of hepatitis B surface antigen or positive hepatitis C antibody test result.
21. A positive Human Immunodeficiency Virus (HIV) antibody test.
22. A positive pre-study drugs of abuse test (not explained by diet or approved concomitant medications).
23. A positive alcohol breath test.

5.3. Screening/Baseline/Run-in Failures

Screen failures are defined as subjects who consent to participate in the clinical trial but are never subsequently randomized. In order to ensure transparent reporting of screen failure subjects, meet the Consolidated Standards of Reporting Trials (CONSORT) publishing requirements, and respond to queries from Regulatory authorities, a minimal set of screen failure information is required including Demography, Screen Failure details, Eligibility Criteria, and Serious Adverse Events (see Section 7.3.1.4).

5.3.1. Re-screening

If a subject fails screening, she may be rescreened one additional time.

5.4. Withdrawal/Stopping Criteria

The following actions must be taken in relation to a subject who fails to attend the clinic for a required study visit:

- The site must attempt to contact the subject and re-schedule the missed visit as soon as possible.
- The site must counsel the subject on the importance of maintaining the assigned visit schedule and ascertain whether or not the subject wishes to and/or should continue in the study.
- In cases where the subject is deemed ‘lost to follow up’, the investigator or designee must make every effort to regain contact with the subject (where possible, 3 telephone calls and if necessary a certified letter to the subject’s last known mailing address or local equivalent methods). These contact attempts should be documented in the subject’s medical record.
- Should the subject continue to be unreachable, only then will she be considered to have withdrawn from the study with a primary reason of “Lost to Follow-up”.

A subject may withdraw from study treatment at any time at her own request, or may be withdrawn at any time at the discretion of the investigator for safety, behavioural or administrative reasons. If a subject withdraws from the study, she may request destruction of any samples taken, and the investigator must document this in the site study records.

5.4.1. Pregnancy Complication Stopping Criteria (Group 1 Only)

Any complication requiring clinical intervention which no longer allows for a vaginal delivery or safe completion of study procedures will be cause for immediate withdrawal from the study. Investigators should continue to manage any pregnancy complication per local guidelines, and record any associated AE/SAE or concomitant medication. This includes the need for additional uterotonic administration.

5.4.2. Anaphylaxis Stopping Criteria

Clinical signs or symptoms of anaphylaxis / allergic reaction to IH oxytocin will be an automatic stopping criterion. Stored serum samples will be analysed for anti-oxytocin antibody analysis for affected subjects as detailed in Section 7.5.2. The samples will be analysed for Immunoglobulin E (IgE)/ Immunoglobulin G (IgG) anti-oxytocin titres \pm biochemical markers of mast cell degranulation (e.g. tryptase) in the event of an anaphylactic / allergic reaction occurring.

5.4.3. QTc Stopping Criteria (Group 2 Only)

- The *same* QT correction formula *must* be used for *each individual subject* to determine eligibility for and discontinuation from the study. This formula may not be changed or substituted once the subject has been enrolled.
- For example, if a subject is eligible for the protocol based on QTcF, then QTcF must be used for discontinuation of this individual subject as well.
- Once the QT correction formula has been chosen for a subject's eligibility, the *same formula* must continue to be used for that subject *for all QTc data being collected for data analysis*. Safety ECGs and other non-protocol specified ECGs are an exception.
- The QTc should be based on single or averaged QTc values of triplicate electrocardiograms obtained over a brief (e.g., 5-10 minute) recording period.

QTcF is proposed to be used for this study. If a subject meets either of the following bulleted criterion below, she will be withdrawn from the study.

- QTcF > 500 msec,
- Change from baseline: Increase in QTcF >60 msec.

Withdrawal of subjects is to be based on an average QTcF value of triplicate ECGs. If an ECG demonstrates a prolonged QT interval, then obtain 2 more ECGs over a brief period of time and then use the averaged QTcF values of the 3 ECGs to determine whether the subject should be withdrawn from the study.

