4.1.5. Length of Stay for All Subjects

Group 1 - Women in TSL

Subjects in Group 1 will be admitted to hospital during labour as part of their routine care, and will be required to remain inpatient for a minimum of 4 hours after receiving any study-related dose of oxytocin. After final PK collection, subjects will be finished with study procedures and the main phase of the study will be considered complete. Discharge from hospital will be determined by the subject's medical provider.

Group 2 - Non-pregnant, non-lactating females of child bearing potential

Subjects in Group 2 will be admitted to the clinical unit prior to dosing on Day 1 and are to remain inpatient until at least 4 hours after dosing. Discharge will occur at the discretion of the investigator.

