4.3. Type and Number of Subjects

Sufficient subjects will be screened such that approximately 20 subjects complete all study procedures in Group 1, and approximately 10 subjects complete all study procedures in Group 2 (approximately 5 in each cohort of Group 2). Refer to Section 6.3 for treatment assignment information.

If subjects prematurely discontinue the study, additional replacement subjects may be recruited and assigned to the same treatment at the discretion of the Sponsor. Replacement subjects will complete all study procedures as outlined in Section 7.1.

If the PK variability between subjects in Group 1 is higher than expected, it may be required to increase the sample size up to a maximum of 10 additional subjects per treatment group for IH and IM. In the event of this, sufficient subjects will be screened such that a maximum of 50 subjects complete Group 1.

If a dose adjustment is required in either group, additional subjects may be recruited such that a full 10 subjects receive the final IH or IV dose. See Section 6.4.1 for more details.

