7.3.1.3. Follow-up of AEs and SAEs

After the initial AE/SAE report, the investigator is required to proactively follow each subject at subsequent visits/contacts. All SAEs, and non-serious AEs of special interest (as defined in Section 4.6.1) will be followed until resolution, until the condition stabilizes, until the event is otherwise explained, or until the subject is lost to follow-up (as defined in Section 5.4). Further information on follow-up procedures is given in [Appendix 3](#).

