7.5.2. Immunogenicity

Blood samples will be taken at the time points specified in the Time and Events Table (Section 7.1) to assess the immunogenicity of oxytocin.

Pre- and post-dose samples will be retained in the event that further immunologic tests are deemed necessary to support observations of unexpected anaphylaxis/hypersensitivity, and / or a PK profile for IH oxytocin in any Dosing Session which is regarded by the GSK Study Team to be reasonably attributable to circulating anti-oxytocin antibodies.

Details of the collection / shipping procedures are provided in the SRM.

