12.2. Appendix 2: Liver Safety Required Actions and Follow up Assessments

Phase I Liver chemistry stopping criteria have been designed to assure subject safety and to evaluate liver event etiology (in alignment with the Food and Drug Administration [FDA] premarketing clinical liver safety guidance).

<http://www.fda.gov/downloads/Drugs/GuidanceComplianceRegulatoryInformation/Guidances/UCM174090.pdf>.

Phase I liver chemistry stopping criteria and required follow up assessments

Liver Chemistry Stopping Criteria – Liver Stopping Event	
ALT-absolute	
ALT\geq3xULN
 
If ALT\geq3xULN AND bilirubin^{1,2} \geq 2xULN (>35% direct bilirubin) or INR >1.5, Report as an SAE.
 
See additional Actions and Follow Up Assessments listed below

Required Actions and Follow up Assessments following Liver Stopping Event	
Actions	Follow Up Assessments

 • Immediately discontinue study treatment • Report the event to GSK within 24 hours • Complete the liver event CRF, and complete an SAE data collection tool if the event also meets the criteria for an SAE² • Perform liver event follow up assessments • Monitor the subject until liver chemistries resolve, stabilise, or return to within baseline (see MONITORING below) 
MONITORING:
 
If ALT\geq3xULN AND bilirubin \geq 2xULN or INR >1.5
 
 • Repeat liver chemistries (include ALT, AST, alkaline phosphatase, bilirubin) and perform liver event follow up assessments within 24 hrs • Monitor subjects twice weekly until liver chemistries resolve, stabilise or return to within baseline • A specialist or hepatology consultation is 	
 • Viral hepatitis serology³ • Blood sample for pharmacokinetic (PK) analysis, obtained within 4h of the last dose⁴ • Serum creatine phosphokinase (CPK) and lactate dehydrogenase (LDH). • Fractionate bilirubin, if total bilirubin\geq2xULN • Obtain complete blood count with differential to assess eosinophilia • Record the appearance or worsening of clinical symptoms of liver injury, or hypersensitivity, on the AE report form • Record use of concomitant medications on the concomitant medications report form including acetaminophen, herbal remedies, other over the counter medications. • Record alcohol use on the liver event alcohol intake case report form 
If ALT\geq3xULN AND bilirubin \geq 2xULN or

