12.5.2. Collection of Pregnancy Information

Group 2 Only

- Investigator will collect pregnancy information on any female subject, who becomes pregnant while participating in this study
- Information will be recorded on the appropriate form and submitted to GSK within 2 weeks of learning of a subject's pregnancy.
- Subject will be followed to determine the outcome of the pregnancy. The investigator will collect follow up information on mother and infant, which will be forwarded to GSK. Generally, follow-up will not be required for longer than 6 to 8 weeks beyond the estimated delivery date.
- Any termination of pregnancy will be reported, regardless of fetal status (presence or absence of anomalies) or indication for procedure.
- While pregnancy itself is not considered to be an AE or SAE, any pregnancy complication or elective termination of a pregnancy will be reported as an AE or SAE.
- A spontaneous abortion is always considered to be an SAE and will be reported as such.

- Any SAE occurring as a result of a post-study pregnancy which is considered reasonably related to the study treatment by the investigator, will be reported to GSK as described in Section 12.3. While the investigator is not obligated to actively seek this information in former study participants, he or she may learn of an SAE through spontaneous reporting.

Any female subject who becomes pregnant while participating

- will discontinue study medication or be withdrawn from the study.

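### Section 5.4.3 withdraws a woman who meets a QTcF criterion from the study rather than from further dosing; read literally, this cuts short her timed ECG and PK data without adding dosing protection

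*Protocol*

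**What the plan says.** Section 5.4.3 applies to Group 2 only. After giving the consequence as "If a subject meets either of the following bulleted criterion below, she will be withdrawn from the study", it repeats it for the confirmatory triplicate: the averaged QTcF is used "to determine whether the subject should be withdrawn from the study". It does not say which assessments continue afterwards.

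Elsewhere the protocol separates stopping treatment from leaving the study. The liver rule (Section 5.4.5) discontinues study treatment, and the first action in Appendix 2 (Section 12.2) is "Immediately discontinue study treatment", followed by required monitoring. For a pregnancy during the study, Section 12.5.2 says that the subject "will discontinue study medication or be withdrawn from the study", which lists the two as alternatives.

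Other sections limit the effect of a withdrawal:

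- Section 4.1.5 has Group 2 subjects "remain inpatient until at least 4 hours after dosing".
- Section 7.3.1.3 says that "non-serious AEs of special interest (as defined in Section 4.6.1) will be followed until resolution", and QTc prolongation is among the risks listed in Section 4.6.1.
- Section 12.3.5 obliges the investigator to arrange further measurements where an adverse event calls for them.
- Section 4.3 says that, after a premature discontinuation, "additional replacement subjects may be recruited and assigned to the same treatment".

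**The concern.** A stopping rule for a single-dose session should prevent the next dose. Once a post-dose ECG has triggered the rule, that session's dose has been given, and only a possible Session 2 dose remains to be stopped. An instruction to give no further study treatment stops it. The same instruction would also hold back a dose after a pre-dose trigger. Withdrawal from the study therefore adds nothing to dosing protection.

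What it can add is loss of data. Section 3.2 makes both ECG change from pre-dose and PK primary for Group 2. Followed as written, the rule ends the timed ECG and concentration series of the woman who had the event, because of the event. Her QTcF course against concentration is the record the study would most want. With about 5 women per cohort, one truncated profile is 1/5 of a cohort's data for that treatment. This governs what sites collect, so samples that are never drawn cannot be recovered in the analysis.

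**Working it through.** The plan gives no figure to reproduce. The check counts scheduled assessments.

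**Inputs**

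- Post-dose PK times, Section 7.1.2, Group 2: 2, 3, 5, 8, 10, 15, 20, 30, 45 min and 1, 1.5, 2, 2.5, 3, 4 h, which is 9 + 6 = 15.
- Post-dose ECGs, same table: 6 per session. The columns do not line up identically in every copy of the table in the protocol file, possibly because of the PDF conversion, so both readings are used. Reading A (current version): 2, 15, 30, 45 min, 1.5 h, 4 h. Reading B (the two oldest versions in the file): 2, 10, 20, 30 min, 1 h, 4 h. The 2 min and 4 h ECGs are common to both.
- Assumption: the decision falls 5 to 10 min after the triggering ECG. Section 5.4.3 gives 5 to 10 min only as an example of the recording period for a triplicate; it is not a stated decision time.
- Rule: every scheduled assessment after the decision is lost.

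**Earliest trigger, at the 2 min ECG**

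- Decision at 2 + 5 = 7 min. PK lost from 8 min to 4 h: 15 − 3 = 12, including Cp10. ECGs lost: 5 under A, 5 under B.
- Decision at 2 + 10 = 12 min. PK lost from 15 min to 4 h: 15 − 5 = 10; Cp10 is kept. ECGs lost: 5 under A; 4 under B (20 min, 30 min, 1 h, 4 h).
- Cp20, Cp30 and the 3 h sample needed for a fully observed AUC(0-3h) are lost in both cases. If sampling stopped at once, with only the 2 min sample drawn, the PK loss would be 15 − 1 = 14.

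**Latest scheduled trigger before 4 h**

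- A, at 1.5 h: PK lost at 2, 2.5, 3 and 4 h = 4. ECG lost: 4 h.
- B, at 1 h: PK lost at 1.5, 2, 2.5, 3 and 4 h = 5. ECG lost: 4 h.

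Earlier triggers lose at least as much, so the minimum is 4 of 15 PK samples, including 3 h, and the 4 h ECG. Under A this holds as long as the decision after a 1.5 h ECG comes before the 2 h sample.

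**Trigger at the 4 h ECG:** no scheduled PK sample or ECG is lost, only the visit.

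**The visit.** Section 7.1.1 places the follow-up 7 to 21 days after the last dose. I found no provision keeping it for a woman withdrawn under Section 5.4.3. The one follow-up rule that names prematurely withdrawn subjects, Section 7.3.4.2, concerns device incidents.

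**The case against.** The strongest reply is that Section 5.4.3 never says that assessments cease on withdrawal, and that the protocol uses the term loosely. Section 5.4 moves from withdrawing from treatment to withdrawing from the study within one paragraph. Section 5.4.1 orders withdrawal from the study and then requires continued management and recording. Section 12.5.2 attaches no different consequence to its two alternatives. So a sensible site might carry on. That is fair, and it is why the point is put as a literal reading. But nothing requires the timed ECGs, the PK samples or the visit, and a site that stopped them would be following the text.

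A second reply is that the effect on the analysis is small. Safety is summarised descriptively (Section 9.4.1.1), PK parameters are derived as the data allow, no hypothesis is tested, data already collected stay in the analysis populations (Section 9.3.1), and a replacement may be recruited. This stands as to size. A replacement can restore the number in the cohort but not the affected woman's later values.

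A third reply is that ending research procedures in a healthy volunteer after a marked QTcF change is a cautious choice. The caution is kept if assessments continue only where not clinically contraindicated.

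The visit also carries the only immunogenicity sample scheduled after the last dose. Little rests on this: "Pre- and post-dose samples will be retained in the event that further immunologic tests are deemed necessary", and Section 7.5.2 ties such tests to hypersensitivity or an antibody-type PK profile, not to a QTc event.

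**Conclusion.** The point holds as a minor one. Section 5.4.3 fixes a consequence wider than its purpose, and the excess falls on primary-endpoint data. On the literal reading, a trigger at a scheduled ECG before 4 h loses at least 4 of 15 PK samples and the 4 h ECG, and every post-dose trigger loses the visit. The 10 to 12 of 15 applies only to the earliest trigger under the assumed decision time and is not a typical loss.

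A reader might infer that safety follow-up of the QTc event stops. The documents do not support that. If the event is recorded as an adverse event, Sections 7.3.1.3 (through 4.6.1) and 12.3.5 probably still require follow-up, and Section 4.1.5 keeps her in the unit for at least 4 h. The triplicate that establishes the event is also taken before any withdrawal.

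No event rate is given, so an expected loss cannot be computed. With a 5 I.U. IV dose and QTcF above 450 msec excluded at entry (Section 5.2), the event is likely rare.

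**What to change.** In both places in Section 5.4.3, replace withdrawal from the study with: *will receive no further study treatment*. Then add: *After a post-dose trigger she completes that session's scheduled ECG, telemetry, vital sign, laboratory and PK assessments unless clinically contraindicated, and attends the 7-21 day follow-up visit; the QTc event is followed until resolution or stabilisation per Section 7.3.1.3.*

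The thresholds and the triplicate rule are unchanged. A requirement to repeat ECGs until QTcF is back at baseline is not needed: it would be open-ended and stricter than Section 7.3.1.3, which also accepts stabilisation.

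The cost is two phrases and one sentence. The session assessments are already scheduled within the inpatient stay, and the visit is already planned. The small downside is continued scheduled sampling in a rarely affected woman. No dosing protection is given up.

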3.2. Group 2: Non-pregnant, non-lactating females of child bearing potential

Objectives	Endpoints
Primary	

 To evaluate the safety and tolerability of IH and IV oxytocin. 	
 General safety parameters: adverse events; absolute values and changes over time of vital signs (blood pressure, heart rate) and 12-lead electrocardiogram (ECG) parameters (PR, QRS, QT, Corrected QT interval [QTc] intervals) from pre-dose values. Specific respiratory safety parameters: adverse respiratory events as monitored by spirometry including Forced expiratory volume at 1 minute (FEV1.0), respiratory rate, and pulse oximetry.

 To characterize the pharmacokinetics of single doses of IH oxytocin and 5 I.U. IV oxytocin. 	
 Plasma concentration time profile for IH oxytocin and 5 I.U. IV oxytocin. PK parameters: C_{max}, C_{p10}, C_{p20}, C_{p30}, t_{max}, AUC, Plasma clearance (CL), volume of distribution and t_{1/2} will be calculated as data permit.
Exploratory	

 To evaluate endogenous plasma oxytocin concentrations in non-pregnant females in the presence and absence of the combined oral contraceptive. 	
 Pre-dose plasma concentrations of oxytocin.

 To compare the IH pharmacokinetics of oxytocin between Cohort A (subjects on combined oral contraceptive) and Cohort B (subjects using a non-hormonal form of contraception). 	
 C_{p10}, C_{p20}, C_{p30}, C_{max}, AUC(0-3h), Area under the concentration-time curve from time zero to infinity (AUC[0-∞]) and t_{1/2}, will be compared as data permit.

 To compare the IV pharmacokinetics of oxytocin between Cohort A and Cohort B. 	
 C_{max}, AUC, t_{1/2}, CL and Volume of distribution (VOD) will be compared as data permit.

[figure not shown]
3.3. Groups 1 and 2: Women in TSL and Non-pregnant, non-lactating females of child bearing potential

Objectives	Endpoints
Exploratory	

 To compare pharmacokinetics of IH oxytocin between Group 1 and Group 2. 	
 Cp10, Cp20, Cp30, Cmax, AUC(0-3h) AUC(0-∞), and t1/2 will be compared as data permit.

[figure not shown]

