7.3.8. Electrocardiogram (ECG) (Group 2 Only)

- Triplicate 12-lead ECGs will be obtained at screening as listed in Section 7.1.1.
- Single 12-lead ECGs will be obtained at each timepoint as listed in Section 7.1.2 using an ECG machine that automatically calculates the heart rate and measures PR, QRS, QT, and QTc intervals. Refer to Section 5.4.3 for QTc withdrawal criteria and additional QTc readings that may be necessary.
- At all single 12-lead ECG time-points if QTc >450, repeat twice and take average reading.

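### The Group 2 ECG-change endpoint rests on one pre-dose tracing per session, and Section 5.4.3 does not say which ECG is the baseline for the 60 msec QTcF criterion

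*Protocol*

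**What the plan says.** All references are to the protocol and to Group 2.

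- **Endpoint (Section 3.2).** The primary safety endpoint includes changes over time in PR, QRS, QT and QTc, with the reference given as "Corrected QT interval [QTc] intervals) from pre-dose values".
- **Number of tracings (Section 7.3.8).** "Triplicate 12-lead ECGs will be obtained at screening as listed in Section 7.1.1". After that, "Single 12-lead ECGs will be obtained at each timepoint as listed in Section 7.1.2". The Section 7.1.2 table lists the pre-dose ECG of both sessions among those time points. There is one exception: at any of them, a QTc above 450 is repeated twice and averaged.
- **Withdrawal (Section 5.4.3).** There are two criteria. One is absolute, "QTcF > 500 msec", and needs no baseline. The other is "Change from baseline: Increase in QTcF >60 msec". For both, "Withdrawal of subjects is to be based on an average QTcF value of triplicate ECGs". The same section also says "The QTc should be based on single or averaged QTc values of triplicate electrocardiograms". It does not define baseline.
- **Timing (Sections 4.1.3.2 and 4.2).** Screening falls within 28 days before the study starts for the woman. Session 2 is recommended within 14 days of Session 1.

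**The concern.** A change score is only as good as its reference value. Here the reference for the primary ECG endpoint is normally one tracing per session, and its error is subtracted from every later reading of that session. A chance-low pre-dose tracing pushes all of that woman's changes up, and a chance-high one pushes them all down. More post-dose tracings cannot average this out. The safeguard in Section 7.3.8 acts in one direction: a reading above 450 is repeated, and a chance-low reading never is.

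The withdrawal criterion has a second problem. It compares a triplicate mean with a baseline that could be either of two ECGs. The screening triplicate is more precise but may be weeks old. The pre-dose tracing is current but normally single. Two people applying Section 5.4.3 in good faith could reach different decisions on the same woman. With about five women per cohort in a two-session crossover, losing one between sessions is noticeable.

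**Working it through.** The protocol states no ECG variance and no error rate for this rule, so there is no figure of its own to reproduce. What follows is the size of the effect under a stated assumption.

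**Inputs**
- Pre-dose tracings: 1 as written (Section 7.3.8), 3 if changed.
- Post-dose tracings: normally 1 for the endpoint (Section 7.3.8), 3 for withdrawal (Section 5.4.3).
- Threshold for change: 60 msec (Section 5.4.3).
- Single-tracing SD of QTcF, s: assumed 5 to 10 msec. Tracings are treated as independent and normal.

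**SD of a measured change.** With k baseline and m post-dose tracings, SD = s × √(1/k + 1/m).

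- Endpoint, k=1, m=1: s√2 = 1.414s. With k=3: s√(4/3) = 1.155s. Reduction: 1 − 1.155/1.414 = 18%.
- Withdrawal against pre-dose, k=1, m=3: s√(4/3) = 1.155s. With k=3: s√(2/3) = 0.816s. Reduction: 1 − 0.816/1.155 = 29%.

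| Assumed s (msec) | Endpoint, single pre-dose | Endpoint, triplicate pre-dose | Withdrawal, single pre-dose | Withdrawal, triplicate pre-dose |
|---|---|---|---|---|
| 5 | 7.1 | 5.8 | 5.8 | 4.1 |
| 8 | 11.3 | 9.2 | 9.2 | 6.5 |
| 10 | 14.1 | 11.5 | 11.5 | 8.2 |

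**Shared error.** Two post-dose changes in one session share the baseline error, with covariance s²/k and variance s²(1 + 1/k). Their error correlation is therefore 1/(k+1): 0.50 with one pre-dose tracing and 0.25 with three.

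**Where it matters for the 60 msec criterion.** P(measured change > 60 | true rise d) = 1 − Φ((60 − d)/SD). This holds if baseline is the pre-dose ECG and the post-dose repeats are taken. Single versus triplicate pre-dose:

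| True rise d | s = 5 | s = 8 | s = 10 |
|---|---|---|---|
| 40 | 0.03% vs <0.001% | 1.5% vs 0.1% | 4.2% vs 0.7% |
| 50 | 4.2% vs 0.7% | 14.0% vs 6.3% | 19.3% vs 11.0% |
| 55 | 19.3% vs 11.0% | 29.4% vs 22.2% | 33.3% vs 27.0% |

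By symmetry, a true rise of 70 is missed as often as a true rise of 50 is called. With no true change, a reading above 60 has probability below 0.001% for s up to 10.

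**The two candidate baselines.** If the screening mean and the pre-dose tracing differ by D, the two computed changes differ by exactly D. Tracing noise alone gives D an SD of s√(1/3 + 1) = 1.155s, or 5.8 to 11.5 msec, before any real drift. The screening ECG may be up to 28 days old at Session 1 and about 28 + 14 = 42 days old at Session 2. When the two candidate changes fall on opposite sides of 60, the decision depends on which baseline is used.

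**The case against.** **A stronger reading is tempting:** that the 60 msec criterion itself sets a post-dose triplicate against one pre-dose tracing, so noise in that tracing drives withdrawals. The protocol does not support this.

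- Section 5.4.3 never ties baseline to pre-dose, and a screening triplicate exists. If that is the baseline, both sides are means of three and the imbalance in the number of tracings disappears.
- It is also not true that every pre-dose ECG is single, because a pre-dose QTc above 450 is averaged over three. This deals with part of the chance-high case, although women with QTcF above 450 are excluded at entry (Section 5.2), so it should be uncommon.
- Noise alone practically never reaches 60 msec at the assumed SDs. A large true rise has to be present already.
- The probabilities above are not the operating characteristics of the written rule. Repeats depend on a trigger ("If an ECG demonstrates a prolonged QT interval, then obtain 2 more ECGs over a brief period of time", or QTc above 450 in Section 7.3.8), so a post-dose triplicate may not exist.

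**For the endpoint,** routine tracings are single on both sides, the summary is descriptive (Section 9.4.1.1), and Section 5.4.3 permits single values. All of that is right. There is no mismatch in the endpoint, only a reference that is noisier than it need be. The derivation of baseline is often left to an analysis plan, but an analysis plan cannot supply tracings that were never recorded, and withdrawal is decided during the study.

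**On consequence,** each woman has two doses in all, so the criterion can affect dosing only between Session 1 and Session 2. The absolute 500 msec criterion does not depend on baseline.

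**Conclusion.** The point holds in two parts. First, the primary ECG-change endpoint rests on one pre-dose tracing per session, corrected only when the reading is high. Under independent tracings with an assumed single-tracing SD of 5 to 10 msec, recording three would cut the measurement SD of each change by 18% and halve the error correlation between changes within a session. If tracings taken minutes apart are positively correlated in their error, the gain is smaller. Second, the baseline for the 60 msec criterion is undefined, with two candidates of different precision and age. The 29% gain for that criterion is conditional on pre-dose being the baseline and on repeats being taken, and it affects classification only for true rises near 60 msec.

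This is an inexpensive improvement to a primary safety measure in about 10 women, together with a gap in the text that has to be closed. It does not show that the withdrawal rule misfires as written.

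**What to change.** In Sections 7.3.8 and 7.1.2, record the pre-dose 12-lead ECG of each session in triplicate, and state in Section 3.2 that its mean is the reference for the change endpoint. The cost is 2 extra tracings × 2 sessions × 10 women = 40 tracings, plus a few minutes before each dose. The ECG is already scheduled and non-invasive.

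Separately, reconcile Sections 3.2, 5.4.3 and 7.3.8 so that the baseline ECG for the 60 msec criterion is named, with the number of tracings on each side. Which baseline or threshold the withdrawal rule should use is a clinical decision for the sponsor and investigator, and no view is given on it here.
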